## 1. Introduction and Purpose

Historically, mechanical methods were the first methods developed to ripen the cervix or to induce labor (1). Dilapan-S®, a hygroscopic cervical dilator made of a patented hydrogel (AQUACRYL), works by absorbing fluid from the cells of the cervical canal, resulting in reversible cell wall dehydration and softening. The increase in volume of the rod(s) in turn, leads by mechanical stretch, to endogenous PG release with resultant cervical ripening. Dilapan-S® is approved by the FDA for cervical ripening in the third trimester. Recently a non-inferiority randomized trial at our center comparing Dilapan-S® to the most commonly used, but not FDA approved, mechanical dilator method (Foley balloon) was completed and results show that it is not inferior to the latter (<https://clinicaltrials.gov/ct2/show/NCT02899689>). The usual practice with mechanical ripening methods is to insert the mechanical dilator in the hospital and then await cervical ripening, which can take up to 12 hours. We believe that allowing the subject to go back home after insertion is a promising strategy that lowers in-hospital healthcare costs and improves subject satisfaction. Therefore, we propose a randomized controlled trial to compare the efficacy and safety of outpatient versus inpatient pre-induction cervical ripening with Dilapan-S® in pregnant women greater than 37 weeks.

## 2. Background

Labor induction is a common obstetric procedure that is generally undertaken when the risks of continuing pregnancy outweigh the benefits (2). To maximize the success of induction of labor in women with an unfavorable cervix, various ripening methods are available. These include pharmacological agents such as prostaglandins and mechanical agents such as the Foley balloon cervical dilator, which has been used in labor delivery units for decades. Mechanical methods of labor induction are safe and cost effective. Recently, Dilapan-S® was approved by the FDA as another form of mechanical dilators. The rates of labor induction continue to increase and a recently completed trial which showed that induction at 39 weeks decreases cesarean delivery compared with expectant management is expected to lead to even higher rates of induction (2). Currently, cervical ripening in the US is performed as inpatient. A few pilot studies and the mechanism of action of mechanical dilators support the safety of allowing women to go home after insertion. There have been multiple proposals to study outpatient cervical ripening (3-7), but none evaluated the role of Dilapan-S® in the outpatient setting. Unlike the Foley balloon, Dilapan-S® is FDA approved for labor induction and does not have any parts that protrude from the vagina, making it the ideal candidate for outpatient cervical ripening. However, data are lacking regarding the comparative effectiveness of inpatient versus outpatient Dilapan-S® in labor induction. Trials are also needed to determine whether outpatient cervical ripening actually shortens length of hospital stay compared with inpatient cervical ripening.

## 3. Concise Summary of Project

The **target population** for our study is women who present for induction of labor. If there is a decision by the obstetrical team to place a mechanical dilator for cervical ripening, the obstetrical team will notify the research staff so that the patient may be screened for the study. If the subject is eligible for the trial, written informed consent will be obtained by person-to-person contact. The PI, study coordinator, or a collaborator will be responsible for the informed consent procedure. After informed consent is obtained and Dilapan-S® is placed, the patient will be randomized to the Outpatient or the Inpatient group. Those randomized to the outpatient group will be asked to come back within 12 hours or sooner if contractions or other conditions arise.

Our **primary objective** will be to compare the hospital length of stay in the inpatient setting to the outpatient setting.

**Secondary objectives** will be to compare other clinical outcomes such as composite maternal and neonatal outcomes, vaginal delivery rate within 24 and 36 hours after admission, time to reach active stage of labor defined as  $\geq 6$  cm, change in Bishop score, rates of spontaneous and operative vaginal delivery, rate of cesarean delivery, adverse events, healthcare cost impact and subject satisfaction.

**Healthcare cost impact** will be assessed based on direct hospital costs or Medicaid charges, using cost minimization technique. In cost-minimization analysis, two or more interventions that have been assumed or shown to have the same effectiveness are compared for cost and the least expensive one is recommended from an economic perspective. The primary analysis will be performed for all those randomized including the costs/charges after randomization. A secondary analysis will be performed accounting separately for costs/charges before randomization.

**Secondary Analysis/ Metanalysis** will be performed for all those randomized as individual participant data meta-analysis all data from respective randomized controlled trials in the different centers, including from UTMB, will be de-identified. All centers will be requested to send the raw data for secondary analysis in an individual participant data meta-analysis. Research groups who share data will get the opportunity of a co-authorship in relation to the size of their study.

Data will be shared in a file that is encrypted and deidentified and password protected.

**Randomization** will be performed using a computer-generated random list of numbers assigning subjects to the 2 groups of the study. This list of random number assignments will be kept secure in an opaque envelope until the end of the study. 2 randomization sequences will be required for UTMB and CUMC sites.

No significant adverse effects are expected with the use of Dilapan-S® for mechanical dilation as an outpatient when compared to inpatient setting. The most common adverse events from cervical ripening with mechanical dilators such as the Foley balloon have been reported to be less than 1% (8), the most common being pain (0.26%), unintended amniotomy (0.04%), vaginal bleeding (0.07%), non-reassuring fetal heart tracing (0.07%), and uterine tachysystole (too low to quantify). Our group also reported the following adverse effects with inpatient use of Dilapan-S® for cervical ripening in a group of 444 subjects (9):

Maternal and neonatal adverse events	Nr. of cases (%)	Comments (n)
Uterine tachysystole	1 (0.2)	
Non reassuring fetal heart rate	1 (0.2)	
Maternal complications/discomfort	15 (3.4)	Bleeding during insertion/extraction of dilators (12), Cramping/pain (1), Other (1)
Uterine contractions	111 (25)	Tocography during cervical ripening showed low frequency and mild intensity contractions
Maternal infection	14 (3.2)	Chorioamnionitis (9), Urinary tract infection (3), Endomyometritis (1), Wound infection (1)

NICU admission	6 (1.4)	Meconium aspiration (2), Growth restriction (2), Asphyxia (1), Congenital cardiac abnormality (1)
Neonatal infection	1 (0.2)	Neonatal sepsis (maternal group B Streptococcus was not observed prior IOL)

The most significant potential risks noted with Dilapan-S® occur during or shortly after insertion and include vaginal bleeding due to cervical trauma and incidental rupture of membranes, as well as pain or discomfort with placement. If these occur and are persistent (i.e. unresolved pain despite analgesia), subjects will be admitted for delivery (as they require maternal monitoring) and will not be randomized, since they do not fulfill the eligibility criteria to receive the outpatient intervention.

Similarly, in the case of inability to place Dilapan-S®, patients will not be randomized and will be considered a screening failure (please refer to section 4.7 for further details). Recent data reports that the risks associated with outpatient pre-induction are similar when compared to inpatient pre-induction cervical ripening (10).

The study period will be between September 2018 and December 2021. The sample size will be up to 376 consented subjects at UTMB and at CUMC (see section 12).

The subject will be withdrawn from the study at any time, if she wishes to discontinue participation and withdraw her consent (refer to section 4.7 for details).

The data collected will be kept on a password-secured UTMB or CUMC computer. An encrypted USB flash drive will be used to transfer data, if needed. The data will be linked to the patient by the patient's MRN number. This identifier is needed to access and analyze demographic data. After analysis of the data, all identifiers will be deleted.

Data to be collected will consist of maternal age and ethnicity, gravida/para, gestational age, height, weight, estimated fetal weight, reason for induction, date and time of device placement, date and time of delivery, mode of delivery, Bishop score at eligibility assessment, Bishop score prior to dilator insertion, Bishop score after removal or expulsion of dilator, date and time of rupture of membranes, date and time of device expulsion/removal, hospital length of stay, other intrapartum and obstetrical interventions, complications in device placement and cervical ripening, during labor and delivery including but not limited to meconium, infections, hemorrhage, fetal decelerations and subject satisfaction. We will also collect the amount of analgesics subjects received during device placement, cervical ripening and induction time (includes acetaminophen or intravenous medications or regional anesthesia). Data will be abstracted from the medical records as well as from direct interview. We will also collect basic neonatal data including birth weight, Apgar scores, rate of admission to neonatal intensive care unit, infections, and other neonatal complications. The data collected will not be used for clinical diagnosis or treatment purposes. Additional economic data to be collected includes the following admission direct costs or charges from the following services/departments: Blood Bank Transfusion Operations, Chemistry Division, Hematopathology Division, JSH Labor & Delivery unit, Materials Management, Microbiology Division, Mother Baby Unit, Pharmacy, Respiratory Care Services, Surgical Operating Suite.

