### **13.4. Sample size**

Sample size was calculated based on the determination of superiority. The primary outcome is proportion of women with hospital stay >48 hours. For the sample size calculation, we assumed the proportion in the control arm would be 54% ( $p_i = 0.54$ ). This is based on current experience at UTMB and unpublished data from an international registry trial (9). We estimate that outpatient intervention would decrease this proportion by 30% ( $p_{ii} = 0.378$ ). Based on 85% power and two-sided alpha of 0.05, the total sample size per group required would be 169. Accounting for 10% of premature terminations or drop outs the sample size per group becomes 188, making the total sample size needed 376.

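### The cost-minimization analysis needs equal effectiveness of the two settings, and the plan gives neither a basis for assuming it nor a way to show it

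*Combined protocol and SAP*

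**What the plan says.** Section 3 (Concise Summary of Project) makes healthcare cost impact a secondary objective, to be assessed on direct hospital costs or Medicaid charges "using cost minimization technique". It then describes the technique in general terms: interventions that "have been assumed or shown to have the same effectiveness are compared for cost and the least expensive one is recommended", the recommendation being made from an economic standpoint. The main cost analysis covers all randomized women and counts costs or charges after randomization.

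On prior evidence, section 2 states that "data are lacking regarding the comparative effectiveness of inpatient versus outpatient Dilapan-S® in labor induction". Section 3 expects no significant adverse effects of outpatient use compared with inpatient use, and cites a report of similar risks in the two settings. By its title in the reference list, that report is a randomized trial of the Foley catheter in parous women.

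On what the trial can show, section 13.4 says "Sample size was calculated based on the determination of superiority", the outcome being hospital stay over 48 hours. Section 13.2 tests that outcome by chi-square. Section 13.3 treats nominal secondary outcomes in the same way, continuous ones by t-test or Wilcoxon-Mann-Whitney, and time-to-event ones by log-rank. Section 6.2 lists caesarean delivery, vaginal delivery, the neonatal composite, maternal and neonatal complications, and charges among the secondary outcomes.

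**The concern.** Comparing arms on cost alone is sound only when effectiveness can be set aside as equal. The protocol states this condition itself, then leaves it without support. It gives no reason to assume equality of effect and describes the evidence as missing. It also gives no margin against which equality could be shown.

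Meanwhile the same trial compares caesarean, vaginal delivery and neonatal outcomes as open questions. The practical risk is that non-significant results on those outcomes are read as having met the condition, so that the economic conclusion rests on cost alone while clinically relevant differences remain compatible with the data. Cost is a named objective, and section 12 presents lower cost as a potential benefit, so the conclusion is likely to be used.

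**Working it through.** **The plan's own figure.** Inputs from section 13.4: control rate p1 = 0.54; 30% relative reduction, so p2 = 0.54 × 0.70 = 0.378; two-sided alpha 0.05; power 85%.

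n = [1.960·√(2p̄(1−p̄)) + 1.036·√(p1(1−p1) + p2(1−p2))]² / (p1−p2)², with p̄ = 0.459.

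This gives (1.381 + 0.721)² / 0.0262 = 168.4, so 169 per group. Then 169/0.9 = 187.8, so 188 per group and 376 in total. The stated figures reproduce exactly, and the sample size is sound for its own purpose.

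**Precision on clinical outcomes.** With equal rates p in both arms, the 95% CI half-width is 1.96·√(2p(1−p)/n). The NICU rate of 1.4% (6 of 444) is from the inpatient registry table in section 3. The documents give no expected caesarean rate, so 15% to 30% is an assumed range.

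| Outcome and rate | n = 169 per arm | n = 188 per arm |
|---|---|---|
| NICU admission, 1.4% | ±2.5 points | ±2.4 points |
| Caesarean, 15% (assumed) | ±7.6 | ±7.2 |
| Caesarean, 20% (assumed) | ±8.5 | ±8.1 |
| Caesarean, 25% (assumed) | ±9.2 | ±8.8 |
| Caesarean, 30% (assumed) | ±9.8 | ±9.3 |

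For example, at 25%: 1.96·√(0.375/169) = 0.092. For NICU admission the half-width exceeds the rate itself, so with equal observed rates a doubling (a difference of 1.4 points) lies inside the interval. At 1.4% only about 2.4 events per arm are expected (169 × 0.014), so the normal approximation is rough there.

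**Power of the planned chi-square test to detect a worsening** (169 to 188 per arm, normal approximation):
- Caesarean 20% to 25%: 19.5% to 21.2%.
- Caesarean 30% to 35%: 16.4% to 17.7%.
- NICU 1.4% to 2.8%: 14.4% to 15.5%.

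A non-significant result is thus the likely outcome even when such a worsening is real.

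**Power to show equivalence.** The plan sets no margin, so ±5 and ±10 points are assumed here. With a true difference of zero, the chance that the 95% CI lies within ±m is 2Φ(m/SE − 1.96) − 1, or zero if that is negative.
- Caesarean at 20% to 30%, ±5 points: 0%.
- Caesarean, ±10 points: 27% to 36% at a 20% rate, and 4% to 12% at a 30% rate.
- NICU at 1.4%, ±5 points: 95% to 97%, but that margin is more than three times the rate (5/1.4 = 3.6).

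For 80% power at caesarean rates of 20% to 30%, equivalence would need about 337 to 442 per arm for ±10 points and 1,345 to 1,766 for ±5 points.

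**The case against.** Several points on the other side stand.

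- A reader might infer that the plan recommends the cheaper arm whatever the clinical results. It does not. The sentence is a general definition, names no arm, applies only where effectiveness is the same, and speaks from an economic standpoint. If the trial found a clinical difference, the condition would fail on its own terms.
- A reader might also infer that superiority on hospital stay contradicts cost-minimization. It does not. Length of stay is a measure of resource use, and a trial can coherently aim for shorter stay with clinical outcomes unchanged, which is the hope stated in section 12.
- The definition allows equality to be assumed. Both arms receive the same device and the same management after ripening, and section 2 points to pilot studies and mechanism of action. This is a rationale, but the cited support concerns mainly safety, and the same section says effectiveness data are lacking.
- The clinical outcomes are already prespecified and compared by arm, and some harm would enter the costs: the listed departments include the operating suite and blood bank. No NICU cost centre is named, so that offset is partial.
- Wide intervals follow from the size of the trial and would be no narrower under another economic method. That is true; the gain is that they would be reported beside the cost result.
- Section 13 defers detail to an SAP to be approved before database lock. The document contains no cost method beyond section 3, so a condition set elsewhere cannot be ruled out.

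None of these supplies a basis for the premise, a margin, or confidence intervals for the clinical differences.

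**Conclusion.** The point holds in limited form. The cost method rests on a premise that the plan neither justifies nor is set up to demonstrate, and non-significant secondary comparisons would not fill the gap. The NICU precision figure uses the document's registry rate; the caesarean figures rest on assumed rates, and the equivalence figures on assumed margins as well.

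It would go too far to say that the trial cannot show equality on any outcome: for rare events a wide margin could be met. The gap is that no margin is prespecified, and for caesarean the planned numbers give little or no power at ±5 or ±10 points over the assumed 20% to 30%. The primary analysis and the sample size are unaffected. This is an inexpensive improvement to a secondary objective.

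**What to change.** In the healthcare cost paragraph of section 3, replace cost-minimization with a cost-consequence analysis, and carry the same text into the SAP. Suggested content: *Mean costs or charges per woman after randomization will be compared between arms as a difference with 95% CI. The result will be presented in one table beside the between-arm differences, each with 95% CI, in caesarean delivery, vaginal delivery, and maternal and neonatal outcomes. No recommendation will be drawn from cost alone.* The existing secondary analysis, which accounts separately for costs before randomization, can stay.

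Keeping cost-minimization would instead require a stated basis for equal effectiveness, or prespecified margins on key clinical outcomes that must be met first. On the figures above the trial would probably miss a ±5 or ±10 point margin for caesarean even with no true difference, so the cost-consequence form is the more practical choice.

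The cost is a wording change and one extra table from data already to be collected, with no change to sample size, design or care. The price is a less categorical economic conclusion.

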## 5. Study Procedures

### VISIT #1

#### 5.1. Screening, eligibility assessment, consenting and baseline data collection

After institutional review board (IRB) approval, pregnant women who have a plan of care for induction of labor at term will be approached by the principal investigator or any of the co-investigators for participation in the study. Informed consent for this study can be obtained during several different phases of interaction with the patient:

Phase 1: At any antenatal obstetrical office visit when decision is made to schedule subject for induction of labor.

Phase 2: Potential subjects presenting for induction of labor at term in the “Labor and delivery” unit (L&D).

Subjects willing to participate in the study will be evaluated for their eligibility including their Bishop score. The latter will be obtained from the medical record after the initial pelvic exam which is standard of care in our unit. Subjects will be reassured that participation in the study is voluntary and will not interfere with diagnosis or treatment of her condition. The subjects will receive the same care and expertise as any other subject treated in our unit. Subjects are approached in a private patient room, and written consent will be obtained by direct person-to-person contact. The principal investigator, study coordinator, or a collaborator will be responsible for the informed consent. Non-English-speaking subjects are anticipated to be part of the study population and informed consent will be provided in their primary language. We will also be using the teach back method; briefly the potential subject will be asked to explain in their own words what they need to know or do, we will also ensure they understand the study and, whenever needed, re-explain to them about the study procedures and risk of participating in the trial. After obtaining informed consent, and Dilapan-S® is successfully placed (see section 4.2) and after 30 minutes period of observation, subjects who remain eligible will be randomized to management as inpatient versus outpatient (see section 4.3).

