#### 5.2. Placement of synthetic osmotic cervical dilator

Placement of the Dilapan-S® will be performed by trained medical personnel. After informed consent is obtained, Dilapan-S® will be placed as follows:

Before the device placement, subjects will undergo continuous cardiotocography (CTG) monitoring for 30 minutes while fetal condition and uterine activity are monitored. The cervix is visualized with a sterile vaginal speculum and cleaned with iodine or chlorohexidine. As many synthetic osmotic cervical dilators (Dilapan-S®, Medicem Technology s.r.o., Kamenne Zehrovice, Czech Republic) as possible are inserted into the cervical canal under direct visualization. Synthetic osmotic dilators are inserted into the cervical canal with special attention to cross through the internal os.

The number of Dilapan-S® rods inserted will vary, depending on the status of the cervix for the particular subject. Synthetic osmotic dilators will be inserted as per manufacturer’s instructions (IFU –

Appendix 1). After insertion, the subject will be evaluated for excessive bleeding, pain or other concerns by the clinical providers (see section 4.4). The synthetic osmotic dilators will be left in place for at least 12 hours, and no longer than 24 hours. Subjects will be instructed, that under no circumstances they should try to remove Dilapan-S® themselves. If subject removes the device herself, such act will constitute protocol deviation and the subject will be assessed for cervical ripening within Intent-to-Treat analysis (see section 4.4 for details) but will not be included in the Per-Protocol-Population analysis.

In the rare event that the Dilapan-S® cannot be inserted or contraindications for outpatient management develop during insertion or during the observation period after the insertion but before randomization (subject changed her mind and desires to stay inpatient, significant vaginal bleeding during insertion, non-reassuring fetal heart rate, rupture of membrane, intractable pain or other concerns the providers or investigators feel that patient cannot be managed as an outpatient), then the subject will not be randomized nor included in the analyses. These subjects will be considered as screening failures and managed as inpatient according to standard practice and under the direction of the clinical team. Refer to section 4.8.1 for further details.

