**Reporting**

The collection of AEs begins at the time the subject is enrolled into the study (eligible subject with signed informed consent).

Reporting will be done in written via the attached Safety Report Form (Appendix 4).

The Investigator is obligated to send the applicable report to the Sponsor within 24 hours of becoming aware of the event to ensure the safety of all participants in the study and to meet regulatory reporting requirements.

Subsequent reporting to the IRB and the corresponding regulatory authorities will be organized by the Sponsor and in accordance with all applicable legal requirements of the concerned country.

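### Does counting 376 as consented women in section 3, but as 188 per group in section 13.4, leave the trial short of its planned power?

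*Combined protocol and SAP*

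**What the plan says.** Section 3 (Concise Summary of Project) states: "The sample size will be up to 376 consented subjects at UTMB and at CUMC (see section 12". Section 13.4 starts from 169 per group for 85% power and continues: "Accounting for 10% of premature terminations or drop outs the sample size per group becomes 188, making the total sample size needed 376".

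Consent comes before randomisation. Section 5.1 allows it as early as this point: "At any antenatal obstetrical office visit when decision is made to schedule subject for induction of labor". After insertion and 30 minutes of observation, "subjects who remain eligible will be randomized to management as inpatient versus outpatient". Women with persistent problems at insertion "will not be randomized, since they do not fulfill the eligibility criteria to receive the outpatient intervention" (section 3). Where the device cannot be placed, "patients will not be randomized and will be considered a screening failure" (section 3). Section 5.2 covers failed insertion and contraindications that arise before randomisation, calls them rare, and says of such a woman: "then the subject will not be randomized nor included in the analyses".

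The primary (ITT) analysis in section 13.1 takes randomised women whose primary outcome was obtained. Section 5.8, on premature terminations, lists screening failure as 5.8.1 and early termination as 5.8.2. Section 5.8.3 says that women who withdraw or stop early are not replaced. It gives no such rule for screening failures.

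**The concern.** Groups exist only after randomisation, so 188 per group reads most naturally as a randomised count. Section 3 attaches the same total to consented women and makes it a ceiling. If recruitment stops at 376 consents and some women fail before randomisation, fewer than 376 are randomised. If the 10% allowance was meant only for losses after randomisation, fewer than 169 per group would then be evaluable and power would drop below 85%. A reader also cannot tell from the text which count ends recruitment, or how much later loss the plan can absorb.

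**Working it through.** **Inputs from section 13.4:** control proportion 0.54; outpatient proportion 0.378 (30% relative reduction, difference 0.162); two-sided alpha 0.05; power 85%; allowance 10%. Section 13.2 specifies a chi-square test.

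**Reproducing the plan's figure.** The mean proportion is 0.459. With the pooled formula:

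n = [1.960 x sqrt(2 x 0.459 x 0.541) + 1.036 x sqrt(0.54 x 0.46 + 0.378 x 0.622)]^2 / 0.162^2 = 168.35, rounded up to 169 per group.

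169 / 0.9 = 187.8, rounded up to 188; 2 x 188 = 376. All three stated figures are confirmed. Inverting the formula gives power of 85.1% at 169 evaluable per group and 88.6% at 188.

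**Loss that 376 consents can absorb.** The target needs 2 x 169 = 338 evaluable women. (376 - 338) / 376 = 38 / 376 = 10.1%. So 376 consents meet the target if total loss from consent to primary outcome is no more than 38 women. Under that reading of the 10%, sections 3 and 13.4 describe the same plan.

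**If the losses are separate.** Let f be the fraction lost before randomisation and g the fraction lost after. Neither is given in the documents, so both are assumptions. Evaluable women = 376 x (1 - f) x (1 - g), split equally.

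| f (before) | g (after) | Evaluable | Power |
|---|---|---|---|
| 2% | 5% | 350.1 | 86.3% |
| 5% | 5% | 339.3 | 85.3% |
| 2% | 10% | 331.6 | 84.5% |
| 5% | 10% | 321.5 | 83.3% |
| 10% | 0% | 338.4 | 85.2% |
| 10% | 10% | 304.6 | 81.3% |

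**A partial anchor for f.** The table of 444 inpatient Dilapan-S users in section 3 lists bleeding at insertion or extraction (12), cramping or pain (1), non-reassuring heart rate (1) and tachysystole (1). That is 15 / 444 = 3.4% even if no woman is counted twice. Not every such event would bar randomisation: section 3 requires problems at insertion to be persistent. At f = 3.4%, 376 x 0.966 = 363.2 are randomised, and 1 - 338 / 363.2 = 6.9% can still be lost afterwards. This anchor does not cover failed placement, change of mind, or women consented antenatally who never reach insertion.

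**Difference between the two stopping counts.** Randomising 376 needs 376 / 0.98 = 383.7, so 384 consents at f = 2% (8 more), or 376 / 0.95 = 395.8, so 396 at f = 5% (20 more).

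**The case for a change.** The best case for a change is that the text supports two readings and picks neither. Section 13.4 applies the 10% per group. Section 5.8.2, whose title is closest to the wording of the allowance, does not list screening failure. Section 13.1 places women who terminated participation among the randomised. Two sites recruit toward one total, and settling the unit would take a line or two. Because consent can be taken at an antenatal visit, loss before randomisation could exceed 5%. At 10% before and a further 10% after, power is 81.3%.

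What stands is that the unit and the scope of the 10% are not spelled out in the available text, and that the 0 to 2 point range is not a bound if early attrition is large. What does not stand is that a figure is wrong or that the trial is short. The heading of 5.8 covers screening failure, so an allowance for premature terminations can fairly include it. The documents give no reason to expect 10% loss after randomisation on top of earlier losses. The outcome is hospital stay from admission to discharge, taken from records, and section 5.4.1 plans to seek release of records for women who present elsewhere.

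The definition of enrolment in the Reporting part of section 10.1 ("The collection of AEs begins at the time the subject is enrolled into the study (eligible subject with signed informed consent") does not help either side. It fixes when adverse event collection starts, not the recruitment target.

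**Conclusion.** No change to the plan is needed. Section 3 is a summary that states an upper limit and refers the reader to the sample-size section. Its reference to section 12 (Potential Benefit) is one of several cross-references that are one number too low; for instance, section 5.1 cites 4.2 and 4.3 for what are now 5.2 and 5.3. The calculation in 13.4 is correct.

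With the 10% read as total loss from consent onward, 376 consents deliver the 338 evaluable women that 85% power requires. With losses of 2% to 5% before randomisation, power falls below 85% in the cases examined only when a full 10% is lost again afterwards, and then by 0.5 to 1.7 points. Consenting 8 to 20 more women would guard against a shortfall that nothing in the documents shows. Settling the unit the other way would only write down a definition, and section 13 already leaves detail of this kind to an SAP due before database lock.

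Whichever count ends recruitment, the rule does not look at outcomes, and women lost before allocation cannot unbalance the arms. Only precision is affected. This conclusion rests on assumed loss rates and on the description in section 5.2 of insertion and observation failures as rare. Heavy attrition after antenatal consent would weaken it.
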